Unified Parkinson Disease Rating Scale ⁴¹	Patient Motor symptom Severity (motor exam only)
Montreal Cognitive Assessment (MOCA) ^{46, 56}	Patient Cognitive Status
Hoehn and Yahr Scale ⁴⁴	Patient Disease Stage (baseline visit only)
Charlson Comorbidity Index ^{61, 66}	Medical Comorbidities (baseline visit only)

Statistical Analysis: The main objective of the study is to determine the comparative effectiveness of interdisciplinary outpatient palliative care versus usual care with a neurologist for PD regarding effects on patient QOL and caregiver burden. The primary outcome variables will be the QOL-AD and the ZBI.^{40, 55} Secondary outcomes (see **Table 2**) include scales for symptom burden, mood, and spiritual wellbeing. Controlling covariates will include gender, age, disease severity (measured continuously using the Unified Parkinson Disease Rating Scale⁶⁷), cognitive dysfunction (measured continuously using the Montreal Cognitive Assessment⁶⁸), and baseline depression (measured continuously using the HADS Depression Subscale⁶⁴). The explanatory variables will be checked for randomization and multicollinearity. Successful randomization should minimize covariate imbalances between groups, but including them in the model can adjust for lingering confounding effects and account for variance in the outcome variable.

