The outcomes will be modeled with mixed regression model analysis, with correlation for repeated measures, at baseline and at 3, 6, 9, and 12 months. The empirical covariance estimator may be used to safeguard against model misspecification. The models will control for time, interaction between treatment and time, and potential baseline confounders, including gender, age, depression, and disease severity. The default model will have linear time trajectories for each treatment group, and linear functions for baseline controlling covariates. The linearity assumptions will be checked. Non-linear functions could be approximated with piecewise linear functions or transforms. The main contrasts will be the difference in areas under the fixed effect change from baseline curves for the palliative and treatment control groups, and the mean difference in change between 6 months and baseline between the groups. Secondary tests will be conducted for the mean difference in change from baseline between the groups at the 3, 9, and 12-month time points. The contrasts, controlled for all covariates, will be tested for significance using T-tests and F-tests, with an alpha level of 0.05. The effect estimates, 95% confidence intervals, and p values will be reported. In the process, the interaction between time and treatment will be tested. If the time trajectories are linear, then all tests are stochastically equivalent to the time by treatment interaction test with one parameter. Binary outcomes and count outcomes will be analyzed with logistic regression and Poisson regression respectively. Generalized mixed models will account for repeated measures. We plan to perform subgroup analyses for patients with dementia, severe disease, and depression and may perform exploratory subgroup analyses depending on primary results.

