Item non-response for the scales will be dealt with using the half rule, or specific scale instructions when available (e.g. QOL-AD⁵⁷). The half rule is the standard method for completing validated scales with missing items when the items are not hierarchical and generally has better performance than more complex imputation methods.⁶⁹ Descriptive statistics will be compiled for missing scales and assessed for patterns. Logistic regression for missingness will be used to demonstrate its dependency on variables. The initial analysis will use the maximum likelihood for all available data for a response variable when data exists for all explanatory variables. In mixed models correlation on repeated outcomes provides some information on the times with missing outcome values. The data will be assumed missing at random. As a sensitivity analysis, joint models will combine the longitudinal outcomes of patient and caregiver proxy reports on the QOL-AD and use their correlations to provide additional values if a subset of the outcomes are missing. Finally, joint models for the longitudinal QOL scale outcomes and the time to drop out will be fit to incorporate drop out information. Even if outcomes for one scale are not missing at random conditional on the observed data, measurements on other scales at the time, or time to drop out, can serve as proxies. Models for different outcomes and time to drop out will be joined through shared covariance structures and/or shared random effects.

The functions in the regression model will be checked for linearity. Piecewise linear functions or transforms can be used to approximate non-linearities. Crossover of group assignment will be treated in different ways and the results will be compared. The primary analysis will use intent-to-treat, but analysis according to actual treatment, with time varying covariates, and adherers only will also be considered. Results

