from models using all available data for a response variable will be compared to the models with missing data methods. The random effects linking together the joint models will be tested. The missing data methods assume missing at random (MAR). Randomization will be checked for baseline variables with summary statistics and two-way tables. Covariates can partially control for deviations from ideal randomization. Homoskedascity and approximate normality for the outcomes will be checked with standard methods. Homoskedascity can be remedied with heterogeneous variance structures or weights. Non-normality should not be much of an issue, unless severe, and can be dealt with using standard methods such as logarithmic transformations. With our sample size the parameter estimates should be consistent and asymptotically normal because of the Central Limit Theorem. All variables will be checked for outliers, and influential outliers will be considered for removal using standard tests (e.g. Cook's D).

Sample Size and Power Considerations: Allowing for up to 25 dropouts per group by the 6-month time point, a two sample T-test with 125 samples per treatment group (250 total) will detect a difference in our continuous outcomes equal to 42% of the standard deviation with 90% power and an alpha level 0.05. This is greater than the suggested minimal clinically significant change for the QOL-AD of 3 points.⁷⁰ For our secondary measure of QOL the difference of half the standard deviation for the PDQ-39 has been suggested in prior studies to be clinically important and detectable with change over time or with outpatient interventions.^{63, 71, 72} For the ZBI, assuming 110 complete dyads per group would diminish our effect size to 44% of the standard deviation with 90% power and an alpha level 0.05. Even a sample of 90 complete dyads would provide an effect size of 0.5 SD/mean. Minimal clinically important differences have not been established for the ZBI but will be estimated in this study using caregiver global impression of improvement and an anchor based approach.⁷³ Notably, prior studies of palliative interventions have found effect sizes of 0.5 SD/mean and greater for the ZBI.¹⁹ The sample size will also enable us to fit models with a large number of parameters and as described below, the longitudinal mixed models and linear time functions will increase our efficiency. Caregivers will be enrolled for each part

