For a longitudinal model with non-linear time trajectories, the difference in area under the change from baseline curve can summarize treatment effect across all times. If the true time trajectory is linear, and we model it as a piece-wise linear function, with a common intercept and knots at each time point, and the outcome is difference in area under the change from baseline curve, then a sample size of 25 per treatment group (50 total) would achieve 90% power with an alpha level of 0.05 and an effect size equivalent to 50% of the standard deviation at 6 months (6 sd*months of area, 0.5 sd on average). A sample size of 125 per treatment group (250 total) would be virtual certain to detect the effect, even for very small alpha levels, and so a Bonferroni correction could be applied to handle multiple comparisons. A sample size of 125 per treatment group (250 total) would achieve more than 90% power with an alpha level of 0.05 and an effect size equivalent to 22.5% of the standard deviation at 6 months (2.7 sd*months area, 0.225 sd on average). For a test of mean difference in change from baseline at 6 months, a sample size 64 per treatment group (128 total) would achieve 90% power with an alpha level of 0.05 and an effect size equal to 50% of the standard deviation. A sample size of 125 per group (250 total) would almost certainly detect the effect. The test would have more than 90% power even after a Bonferroni adjustment for almost 50 tests. Alternatively, 125 samples per group (250 total) could detect an effect equal to 36% of the standard deviation with 90% power and an alpha level of 0.05. Alternatively, for our minimal dyad size of 90 samples per group (180 total) we could detect an effect equal to 42% of the standard deviation with 90% power and an alpha level of 0.05. All sample size calculations for longitudinal data models assume a compound symmetric covariance structure and a correlation of 0.5 for repeated measures on a participant which is relatively conservative for QOL measures.⁶⁹

Aim 2: Describe the effects of an interdisciplinary outpatient palliative care intervention on patient and caregiver costs and service utilization.

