Sample Size and Power Calculations: In a situation where the treatment effect interacted with a binary variable, and the sample was evenly distributed among the four combination of treatment and the interacting binary variable, achieving 80% power with an alpha level of 0.05 and 63 samples in each combination (252 total) would require a difference in treatment effect equal to 71% of the standard deviation. Alternatively, a

sample of 252 total would be able to detect an increase in the R^2 statistic of the regression model of 0.031 with 80% power and an alpha level of 0.05. A test for the treatment effect within a subgroup of half the sample (126 out of 252, 63 palliative care and 63 standard care patients), with an alpha level of 0.05, would require effect sizes of 51% and 59% of the standard deviation to achieve 80% and 90% power respectively.

Longitudinal mixed models and linear time functions however would increase this efficiency. For a model with piece-wise linear functions for the time trajectories, with knots at each time point, and in a situation where the true time trajectories are linear, the treatment effect interacts with a binary variable, and the sample was evenly distributed among the four combinations of treatment and the interaction binary variable, a sample size of 63 in each combination (252 total) could achieve 90% power with an alpha level of 0.05 and a difference in treatment effect equal to 44% of the standard deviation at 6 months (5.3 sd*months area, 0.44 sd on average). A test for a treatment effect within a subgroup of half the sample could achieve 90% power with an alpha level of 0.05 and a treatment effect equal to 32% of the standard deviation at 6 months (3.8 sd*months area, 0.32 sd on average). If the time functions are linear, and linear slopes are used for the model, then 252 samples, equally partitioned among the combinations, could detect, with 90% power, a difference in treatment effect of 32%, and a within group treatment effect of 23%, of the standard deviation at 6 months. The sample size calculations for longitudinal data models assume a compound symmetric covariance structure and a correlation of 0.5 for repeated measures on a participant. Adjusting for multiple comparisons would make the individual tests more conservative. A model with linear time functions eliminates the need for comparisons at different time points.

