5) *Will results be biased without blinding?* It is impossible to truly blind an intervention of this nature. We have used patient-reported outcomes to increase the relevance of results as there are no objective biomarkers relevant to our research questions. Despite this, prior multidisciplinary and palliative intervention trials have reported negative results suggesting that blinding biases do not overwhelm clinical effects.⁴⁴

Future Directions

If this intervention is successful in improving patient QOL and/or caregiver distress we would plan to explore alternate delivery methods to improve the efficiency and dissemination of this approach including telemedicine, group visits, smaller teams and mixed approaches (e.g. in person physician visit and telehealth counseling). Cost-effectiveness studies would also be an important follow-up question to influence system level decisions for this model of care. Lastly, application to other progressive neurological illnesses, including mixed populations, may be warranted as patients with advanced chronic neurological illness tend to be similar in terms of symptoms and needs.

If this intervention is not successful, future studies would be guided by the results of Aim 3. Benefits found in specific subgroups would suggest a need for the development of better screening instruments, while poor responses across the sample would suggest a need for a different model. High drop-out rates or noncompliance with the intervention would suggest a need for alternate delivery methods.

HUMAN SUBJECTS

1. Risks to Human Subjects

1.a. Human Subjects Involvement, Characteristics and Design

Due to the nature of our research questions regarding clinical, psychosocial and spiritual needs in PD patients and their family caregivers we feel that involvement of human research subjects is necessary and justified. As we will discuss below, the risks of this research to human subjects are minimal and the potential for benefit for the involved human subjects, other people and family members living with PD, and society is significant.

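### The Aim 1 plan lets influential outliers be considered for removal without a cut-off or unit of deletion, and does not say that the full-data result stays primary.

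*Combined protocol and SAP*

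**What the plan says.** All references are to the combined protocol and SAP.

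- **Outlier sentence** (Aim 1, Statistical Analysis, model checks just before the sample size section): "All variables will be checked for outliers, and influential outliers will be considered for removal using standard tests", with Cook's D in brackets as an example. The section concerns the primary outcomes QOL-AD and ZBI and does not exempt them.
- **Intent-to-treat** (same section): "The primary analysis will use intent-to-treat, but analysis according to actual treatment" and adherers-only analyses may also be considered. The preceding sentence is about participants who cross over between arms.
- **Data used** (same section, missing-data paragraph): "The initial analysis will use the maximum likelihood for all available data for a response variable when data exists for all explanatory variables".
- **Comparison of results** (same section): fits to all available data are to be compared with fits that use missing-data methods. No comparison with outlier-deleted fits is mentioned.
- **Model** (same section): "The default model will have linear time trajectories for each treatment group", tested at alpha 0.05.

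**The concern.** Three things that decide the result are open: the cut-off, the unit of deletion (visit or participant), and whether the full or the reduced data set gives the headline result.

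This matters in two ways. First, removing the points furthest from the fitted line shrinks the residual variance by construction, so the reported standard error can understate the true variability of the estimate. Second, if the choice of data set is left until results by arm are known, there are several chances to cross the 5% threshold. Extreme scores may also be genuine here: participants are selected for high risk of poor outcomes, and the plan itself describes the population as heterogeneous.

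**Working it through.** **1. Reproduce the plan's own figure.** Inputs: compound symmetry with correlation 0.5 (Aim 1 and Aim 3 sample size sections), visits at 0, 3, 6, 9 and 12 months, linear slopes, common intercept. Put time in units of 6 months, t = 0, 0.5, 1, 1.5, 2, with sum 5 and sum of squares 7.5. With V = 0.5I + 0.5J (I identity, J all ones), V⁻¹ = 2(I − J/6), so t'V⁻¹t = 2(7.5 − 25/6) = 6.667. The variance of the 6-month treatment difference is 2/(6.667n) = 0.3/n.

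At n = 63 per group: SE = √(0.3/63) = 0.0690. The effect with 90% power is (1.960 + 1.282) × 0.0690 = 0.224 SD. For an interaction between two such halves it is √2 × 0.224 = 0.316 SD. Aim 3, Sample Size and Power Calculations, gives "a difference in treatment effect of 32%, and a within group treatment effect of 23%, of the standard deviation at 6 months". The model used below is therefore the plan's linear-time model.

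**2. Why the standard error becomes too small.** A simple case: 6-month value regressed on arm and baseline, 125 per group, correlation 0.5, no true effect, normal errors, 10,000 simulated trials.

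- Full data: mean reported SE 0.1097, actual SD of the estimate 0.1102, type I error 5.2%.
- After deleting Cook's D > 4/n (about 12 of 250): mean reported SE 0.1002, actual SD 0.1206.

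The ratio is 0.1002/0.1206 = 0.831. A nominal 1.96 then acts as 1.96 × 0.831 = 1.63, and 2 × [1 − Φ(1.63)] is about 10.3%. The simulated rate is 10.4%. With t5 and skewed errors it is 8.2% and 8.4%. At D > 1 almost nothing is deleted and the rates stay at 5.2, 5.0 and 5.1%.

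**3. The default linear-time model.** Null trials, 250 participants, 5 visits, correlation 0.5, 6-month contrast, two-sided 5% (sidedness assumed). Assumed rule: every point with Cook's D > 4/n is deleted, with n = 1,250 observations or 250 participants. Rejection rates in %:

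| Setting | Full | Observations deleted | Participants deleted | Any of the three |
|---|---|---|---|---|
| 5 covariates, common intercept, normal | 5.0 | 6.6 | 6.4 | 9.3 |
| same, t4 | 5.2 | 5.7 | 6.2 | 10.0 |
| same, skewed | 5.2 | 6.1 | 6.0 | 9.6 |
| 5 covariates, separate intercepts, normal | 5.4 | 7.3 | 5.5 | 8.9 |
| same, t4 | 4.8 | 5.7 | 4.8 | 8.9 |
| same, skewed | 5.5 | 5.7 | 5.3 | 8.8 |
| No covariates (range over settings) | 3.9–4.9 | 5.7–9.9 | 4.7–6.6 | 9.6–12.5 |

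The covariate rows use REML and 8,000 trials each (Monte Carlo SE 0.2 to 0.3 points). A separate run with a moment estimate of variance, 4,000 trials per setting, normal and t4 errors, gave 4.5–5.3, 5.0–6.6, 4.8–6.4 and 8.1–9.2. Over all runs, the last three columns span 5.0–9.9, 4.7–6.6 and 8.1–12.5.

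**4. What the open items change.** In the runs with covariates, 4/n removes on average 9 to 16 of 1,250 observations, or 9 to 11 of 250 participants. If the flags come instead from an ordinary least-squares fit that ignores the repeated measures, the same 4/n flags about 63 of 1,250 observations (5%), lying in about 51 of 250 participants (21%). At D > 1, any point is flagged in at most 0.05% of trials. Naming Cook's D does not fix the rule.

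**The case against.** The strongest reply is that the sentence commits to nothing. Outliers are only to be considered for removal, the primary analysis is not named, and the same section promises intent-to-treat and an initial analysis of all available data. Removing randomised participants would sit badly with both. This stands in part: full data first is a natural reading. But those sentences were written about crossover and missing data. If they are read as forbidding deletion, they contradict the outlier sentence, and a clarifying line is needed either way.

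A second reply is that the figures come from assumptions. That is correct. In the default model with covariates, observation deletion adds 1.6 to 1.9 points with normal errors but only 0.2 to 0.9 with heavy-tailed or skewed errors, and the smallest rise is within simulation error.

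Three stronger inferences should be resisted.

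- A reader might take the plan's statement "It is impossible to truly blind an intervention of this nature" to mean that outlier review will be unblinded. That statement, under Potential Problems and Alternative Strategies, concerns the intervention. It says nothing about who reviews the data, and a review masked to arm remains possible in an open trial.
- A reader might treat the figure for reporting any of the three results as a ceiling. It is not, because the cut-off is open too.
- A reader might conclude that deleting whole participants is harmless. With separate intercepts the rate barely moves (−0.2 to +0.1 points), but with a common intercept it rises by 0.8 to 1.4 points.

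**Conclusion.** The gap is real and worth closing. The plan permits deletion in the Aim 1 analysis without a rule and does not protect the full-data result.

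The harm is modest and conditional. It requires that deletion is actually carried out, at a cut-off as strict as 4/n, or that the choice of result is left until results by arm are seen. Under those assumptions the 5% level becomes roughly 5 to 10% (observations), 5 to 6.6% (participants) or 8 to 12% (any result reportable). Under D > 1 nothing changes. The documents do not show that points will be removed from the primary analysis, so this is a recommended clarification and does not invalidate the analysis.

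**What to change.** In the Aim 1 Statistical Analysis section, replace the outlier sentence with a rule along these lines: the primary intent-to-treat analysis keeps every valid QOL-AD and ZBI value and corrects only verified data errors; deletion of influential points is reported only as a sensitivity analysis, with the statistic, the cut-off and the unit (observation or participant) fixed in advance.

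The cost is a few lines of SAP text and trivial programming, with no new data. The downside is that genuine extreme scores stay in the primary estimate, with a slightly larger standard error. In the linear-time simulation with covariates, deleting single observations cut the reported standard error by about 2% with normal errors and 8 to 10% with t4 errors. Part of that gain is spurious, so less is given up than it appears.
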